Clinical Study Protocol

Drug Substance	Dapagliflozin
Study Code	D1690L00067
Version	3
Date	07 June 2016

Effects of Dapagliflozin Compared with Glimepiride on Body Composition in Patients with Type 2 Diabetes Inadequately Controlled with Metformin

Sponsor:

AstraZeneca, [name]

VERSION HISTORY

Version 3.0, 07 June 2016

Protocol Synopsis (National Co-ordinating Investigator, NCI): The national co-ordinating investigator was changed and the name, address, e-mail were updated to reflect the new NCI.

Protocol Synopsis (No. of study sites and timeline): the number of study sites was increased from 15 to 17, and the estimated date of last subject completed was updated in accordance with the current recruitment status.

List of Abbreviations and Definition of Terms: a few abbreviations were added.

Section 2.2 (Secondary objectives): A secondary objective was added to evaluation the effect on lean volume of dapagliflozin compared to glimepiride in subjects with type 2 subjects. Accordingly, changes in lean mass from baseline using Dual Energy X-ray Absorptiometry (DXA) scan (baseline, 52 weeks) was added as the outcome measure for the additional objective.

Section 3.1 (Inclusion criteria): The HbA1c range for the inclusion in the study was modified to reflect the HbA1c range found in patients with type 2 diabetes and insufficient glycemic control in the real-world clinical setting.

Section 3.2 (Exclusion criteria): Patients with any kind of surgery using foreign metallic materials was added as an exclusion criterion to facilitate accurate readings of DXA scan results.

Section 3.3 (Subject enrolment and randomization): The word 'approximately' was added as it refers to an estimated number of enrolled patients.

Section 4 (Study plan and timing of procedures): The word 'CT' was added for clarification; and the HbA1C range was modified to reflect the latest change in the inclusion criteria of the study.

Section 5.1.1 (Efficacy assessments – DXA): Evaluation of lean mass was added as it was added as a secondary objective.

Section 5.1.2 (CT): The number and location of slices required for analysis was changed for improved CT analysis.

Section 5.1.5 (Pulse and Blood Pressure): Changes were made to allow the pulse, blood pressure, and blood sample collection to be performed in any order.

Section 5.2.3 (Hypoglycemic event): The error in cross-reference was corrected.

Section 6.3.3 (Variable): The error in cross-reference was corrected.

Section 6.9 (Investigational product and other treatments): This section was moved to a separate level-1 heading, Section 7.0 and thereafter.

Section 7.7.1 (Prohibited medication): The error in cross-reference was corrected.

Section 7.5.2 (Analysis of the secondary variable): The analysis method for the additional secondary variable, 'changes in lean mass from baseline using DXA from baseline to 52 weeks,' was added.

Version 2.0, 2nd November 2015

Section (Protocol Synopsis - Timeline): The timeline was modified to reflect more realistic timeline.

Section (Protocol Synopsis – Objectives): 75g-OGTT related endpoint was deleted, and the secondary endpoints in the secondary objective no. 4 was moved to the secondary objective no. 1.

Figure 1. Study Flow-chart: The study flow chart was modified to reflect the changed allowed dose range of Metformin prior to randomization.

Section 3.1 (Inclusion criteria): Metformin dose range to be eligible for participation in the study was modified to reflect the practical dose of Metformin which patients with type 2 diabetes who is controlled inadequately with Metformin monotherapy take in real clinical practice; and specific descriptions to clarify eligibility criteria for Women of Childbearing potential (WOCBP).

Section 3.2 (Exclusion criteria): Breast-feeding patients as an exclusion criterion and statements that unstable body weight will be judged by investigator, and alcohol and drug abuse will be judged by physician, were added; Exclusion criteria were made more specific for clarification.

Table 1. Study Flow-Chart: Visit window for screening visit was changed to 7 days based on routine practice. Urinalysis was added to be performed on every visit. Candidates for pregnancy test was specified. The DPP-4 inhibitor as a rescue medication was specified as sitagliptin.

Section 5.1.2 (CT): The CT imaging method was modified to improve the reproducibility and reliability of CT scan results.

Section 9.2 Subject Data Protection: Detailed description was added for clarification.

Section 9.4 Informed Consent: Detailed description regarding the environment in which the

Clinical Study Protocol
Drug Substance Dapagliflozin
Study Code D1690L00067
Version 3
Date 07 June 2016

consent should be obtained was added.

Version 1.0, 31st June 2015

Initial creation

Clinical Study Protocol
Drug Substance Dapagliflozin
Study Code D1690L00067
Version 3
Date 07 June 2016

This submission document contains confidential commercial information, disclosure of which is prohibited without providing advance notice to AstraZeneca and opportunity to object.

This Clinical Study Protocol has been subject to a peer review according to AstraZeneca Standard procedures. The clinical study protocol is publicly registered and the results are disclosed and/or published according to the AstraZeneca Global Policy on Bioethics and in compliance with prevailing laws and regulations.

PROTOCOL SYNOPSIS

Effects of Dapagliflozin Compared with Glimepiride on Body Composition in Patients with Type 2 Diabetes Inadequately Controlled with Metformin

National Co-ordinating Investigator

Name [name], PhD
 Title Professor
 Address Department of Endocrinology and Metabolism, Ajou University School of Medicine, [name]
 [name],
 [name]
 [name]
 Email [Redacted](#)

Study site(s) and number of subjects planned

No. of total randomized subjects 120
 No. of total enrolled subjects approximately 160
 No. of study sites 17

Study period	Phase of development	
Estimated date of first subject enrolled	4Q 2015	IV
Estimated date of last subject completed	4Q 2017	

Study design

12-months, randomized, open-label, parallel-group, multi-centres phase IV study

Objectives

Primary Objective:	Outcome Measure:
To evaluate the effect of dapagliflozin on body composition in Korean T2DM subjects.	Changes in total body fat mass from baseline using Dual Energy X-ray Absorptiometry (DXA) scan in 52 weeks after the start of the treatment

Secondary Objective:	Outcome Measure :
Evaluate the efficacy in improving glycaemic control of dapagliflozin compared to glimepiride in subjects with type 2 diabetes.	The change in HbA1c levels from baseline to 52 weeks (baseline, 12, 24, 36 and 52 weeks)
	The proportion of Subjects achieving a glycemic response, defined as HbA1c <7.0% at Week 52
	The change in FBS levels from baseline to 52 weeks (baseline, 4, 12, 24, 36 and 52 weeks)
Evaluate the effect on body weight of dapagliflozin compared to glimepiride in subjects with type 2 diabetes.	Changes in body weight, waist circumference, BMI from baseline (baseline, 4, 12, 24, 36 and 52 weeks)
Evaluate the effect on blood pressure of dapagliflozin compared to glimepiride in subjects with type 2 diabetes.	Changes in SBP and DBP from baseline (baseline, 4, 12, 24, 36 and 52 weeks)
Evaluate the effect on adipose tissue and lean volume of dapagliflozin compared to glimepiride in subjects with type 2 diabetes.	Changes in abdominal VAT and SAT volume, VAT/SAT ratio using abdominal CT from baseline (baseline, 52 weeks)
	Changes in lean mass from baseline using Dual Energy X-ray Absorptiometry (DXA) scan (baseline, 52 weeks)
Evaluate the effect on insulin resistance of dapagliflozin compared to glimepiride in subjects with type 2 diabetes.	Changes in high-sensitivity CRP (hsCRP) and adiponectin from baseline (baseline, 52 weeks)

[figure not shown]
Safety Objective:	Outcome Measure :
Evaluate the safety of dapagliflozin and glimepiride	Changes in CBC, electrolytes, lipid, urinalysis from baseline (baseline, 4, 12, 24, 36 and 52 weeks)
	Number, frequency and proportion of Subjects exposed to adverse events
	Number, frequency and proportion of Subjects exposed to hypoglycemic events

Target subject population

The study population of this study consists of patients with type 2 diabetes who are 19 - 75 yrs old male or female with HbA1c ≥ 7.0 and $< 10.0\%$ in recent 4 weeks.

Altogether 120 patients in 17 study sites will be randomized to this study.

Duration of treatment

Investigational product, dosage and mode of administration

Investigational Product

Dapagliflozin tablets, 10 mg, administered orally, once daily as add-on to metformin 1000 mg.

Comparator

Glimepiride tablets, 1 mg, administered orally 1 or 2 tablets (1mg or 2mg) as add-on to metformin 1000 mg will be used at a dose of 1 to 2 mg/day with the up-titration. Glimepiride dose can be down-titrated at any time to prevent hypoglycemia.

Statistical methods

The full analysis set will include all randomized subjects who receive at least one dose of study medication during the 52 weeks treatment period who have a non-missing baseline value and at least one post-baseline value for primary efficacy variable. Baseline demographic data will be presented in a descriptive manner. Primary endpoint, change in total body fat mass in each treatment arm, will be analyzed with an analysis of covariance (ANCOVA) model. As for the other endpoints, mixed model repeated measures (MMRM) or ANCOVA will be used for continuous variables or logistic regression for binary variable. If any outcome variables are inappropriately distributed, non-parametric methods will be used accordingly. The statistical significance levels for secondary endpoints will not be adjusted for multiple hypothesis testing and will be interpreted only descriptively.

	PAGE
TITLE PAGE	1
VERSION HISTORY	2
PROTOCOL SYNOPSIS.....	6
TABLE OF CONTENTS.....	9
1. INTRODUCTION	15
1.1 Background and rationale for conducting this study	15
1.2 Rationale for study design, doses and control groups.....	15
1.3 Benefit/risk and ethical assessment.....	15
1.4 Study Design.....	16
2. STUDY OBJECTIVES.....	17
2.1 Primary objective	17
2.2 Secondary objectives	17
2.3 Safety objectives	18
2.4 Exploratory objectives	18
3. SUBJECT SELECTION, ENROLMENT, RANDOMISATION, RESTRICTIONS, DISCONTINUATION AND WITHDRAWAL.....	18
3.1 Inclusion criteria	18
3.2 Exclusion criteria	19
3.3 Subject enrolment and randomization	20
3.4 Procedures for handling incorrectly enrolled or randomized subjects.....	20
3.5 Methods for assigning treatment groups.....	21
3.6 Methods for ensuring blinding.....	21
3.7 Methods for unblinding.....	21
3.8 Restrictions	21
3.9 Discontinuation of investigational product.....	21
3.9.1 Procedures for discontinuation of a subject from investigational product	22
3.10 Criteria for withdrawal.....	22
3.10.1 Screen failures.....	22
3.10.2 Withdrawal of the informed consent.....	22
3.11 Discontinuation of the study	23

4.	STUDY PLAN AND TIMING OF PROCEDURES.....	23
4.1	Screening: VISIT 1	28
4.2	Randomization: VISIT 2	28
4.3	Treatment Period: VISITS 3, 4, 5, 6	29
4.4	End of Treatment: VISIT 7	30
4.5	Lack of Glycaemic Control, Rescue Therapy	30
5.	STUDY ASSESSMENTS	31
5.1	Efficacy assessments.....	32
5.1.1	Dual Energy X-Ray Absorptiometry (DXA)	32
5.1.2	CT	32
5.1.3	Height, Weight and Waist Circumference	32
5.1.4	BMI	33
5.1.5	Pulse and Blood Pressure	33

SDT	Study Delivery Team
SGLT1	Sodium-dependent Glucose Transporter 1
SGLT2	Sodium-dependent Glucose Transporter 2
SU	Sulphonylurea(s)
TG	Triglyceride
TSH	Thyroid-stimulating Hormone
UACR	Urine Albumin:Creatinine Ratio
ULN	Upper Limit of Normal
WBDC	Web Based Data Capture
WOCBP	Women of child bearing potential

1. INTRODUCTION

1.1 Background and rationale for conducting this study

Metformin is recommended as a first-line therapy for patients with type 2 diabetes (T2DM). When glycemic control deteriorates, patients with T2DM usually require additional anti-diabetic agents to control glycemia. Sulfonylureas (SUs) such as glimepiride are commonly added to metformin as a second-line treatment in clinical practice when metformin monotherapy cannot adequately control glycemia. However, SUs are frequently associated with unwanted side effects such as weight gain and hypoglycemia.

Therefore, in the present study, we would like to study the effect of dapagliflozin treatment for 52 weeks on body composition in Korean T2DM subjects whose average body mass index (BMI) is around 25 kg/m². The aim of this study is to compare the influence of dapagliflozin on body composition such as total-body fat mass (FM), abdominal visceral adipose tissue (VAT) and subcutaneous adipose tissue (SAT) volume compared with that of glimepiride. We expect that dapagliflozin treatment will decrease total body weight (TBW), and FM, whereas glimepiride increase them. We speculate in the present study that relative changes in body composition (i.e. fat mass vs. lean mass, VAT vs. SAT) may differ from those of the studies in Caucasians. In accordance with the changes of body composition, we predict that not only insulin resistance but also insulin secretion will improve in the dapagliflozin treatment group.

Until now, there has not been any comparative study about the influences of dapagliflozin vs. glimepiride in this area. Considering SUs are widely used in Asians, especially in Koreans, comparison of dapagliflozin vs. glimepiride on the changes of body composition, and insulin resistance and insulin secretion will give an important clinical implication in the management of diabetes, particularly in non-obese Koreans.

1.2 Rationale for study design, doses and control groups

Parallel group study design was chosen. In order maintain the practicality of the phase IV study, open label design of study drug delivery was chosen. The reading of the DXA scans will be conducted by one expert in blinded manner.

Glimepiride is the most frequently used SUs in Korea and therefore this was chosen as comparator.

Dapagliflozin treatment will be associated with reduction of total body FM, BW, abdominal VAT and SAT volume compared with glimepiride.

1.3 Benefit/risk and ethical assessment

Dapagliflozin, a newly developed sodium-glucose cotransporter 2 (SGLT2) inhibitor, improved glycemic control in patients with T2DM when used as monotherapy or as add-on to metformin^[1,2]. SGLT2 inhibitors can reduce hyperglycemia by increasing urinary glucose

excretion^[3]. Since the mechanism of SGLT2 inhibitors is independent of insulin action, dapagliflozin treatment is associated with a low risk of hypoglycemia as well as moderate weight loss compared with SUs treatment^[4].

Recently, Bolinder et al.^[5] have shown that dapagliflozin treatment was associated with reduction in TBW, waist circumference, total-body FM, abdominal VAT and SAT volume in patients with T2DM. In this study of obese Caucasian subjects whose average BMI was 32 kg/m², the two-thirds of weight loss observed with dapagliflozin treatment was attributable to the reduction in total fat mass as measured by DXA, and moreover, dapagliflozin significantly decreased both abdominal VAT and SAT volumes as measured by magnetic resonance spectroscopy. However, the influence of dapagliflozin on change of body composition has not been studied in Asians, who have lower BMI and relatively higher proportion of visceral fat mass compared to Caucasians. Recent data from the 2011 Korea National Health and Nutrition Examination Survey showed that about half of T2DM subjects in Korea are non-obese, even with obesity defined as a BMI of more than 25 kg/m²^[6]. Moreover, Asians appear to have the high proportion of body fat and prominent abdominal obesity compared to Caucasians with similar BMI values^[7,8].

[figure not shown]
While both insulin resistance and β -cell dysfunction are important components in the pathophysiology of T2DM, the relative contributions of these two factors appear to be variable in different populations^[9]. In Asians, the contribution of impaired β -cell function has been suggested to play a more crucial role in the pathogenesis of T2DM compared with Caucasians. In a series of analysis of recent pancreatectomized samples from a Korean university hospital, the pancreatic β -cell mass in T2DM subjects was significantly reduced compared with BMI-matched normal subjects, and β -cell area correlated with some parameters of β -cell function^[10,11]. This might be a reasonable explanation for the fact that insulin secretagogues such as SUs are popular anti-hyperglycemic treatments in Asian diabetic patients.

Compared with SUs, we do not know much about the influence of dapagliflozin on insulin secretion in patients with T2DM. A recent study showed that dapagliflozin treatment had a beneficial effect on insulin resistance, but insulin secretion with only borderline significance^[12]. In this study, dapagliflozin treatment was associated with improved insulin resistance which was evidenced by the reduction in TBW as well as a significant increase in glucose disappearance rate during hyperinsulinemic euglycemic clamps. The borderline increase in insulin secretion might be secondary to the improvement of insulin resistance. However, it has not been thoroughly studied yet.

1.4 Study Design

This is a 52 weeks, randomized, open-label, parallel-group, multi-centres phase IV study. Participants will be randomized 1:1 to receive dapagliflozin 10 mg qd or glimepiride 1~2 mg qd in an open-label manner for 12 months as add-on to metformin 1000 mg.

Figure 1 Study Flow Chart

2. STUDY OBJECTIVES

2.1 Primary objective

Primary Objective:	Outcome Measure:
To evaluate the effect of dapagliflozin on body composition in Korean T2DM subjects.	Changes in total body fat mass from baseline using DXA scan in 52 weeks after the start of the treatment

2.2 Secondary objectives

Secondary Objective:	Outcome Measure :
To evaluate the efficacy in improving glycaemic control of dapagliflozin compared to glimepiride in subjects with type 2 diabetes.	The change in HbA1c levels from baseline to 52 weeks (baseline, 12, 24, 36 and 52 weeks)
	The proportion of Subjects achieving a glycemic response, defined as HbA1c <7.0% at Week 52
	The change in FBS levels from baseline to 52 weeks 52 weeks (baseline, 4, 12, 24, 36 and 52 weeks)
Evaluate the effect on body weight of dapagliflozin compared to glimepiride in subjects with type 2 diabetes.	Changes in body weight, waist circumference, BMI from baseline 52 weeks (baseline, 4, 12, 24, 36 and 52 weeks)
Evaluate the effect on blood pressure of dapagliflozin compared to glimepiride in subjects with type 2 diabetes.	Changes in SBP and DBP from baseline 52 weeks (baseline, 4, 12, 24, 36 and 52 weeks)
Evaluate the effect on adipose tissue and lean volume of dapagliflozin compared to glimepiride in subjects with type 2	Changes in abdominal VAT and SAT volume, VAT/SAT ratio using abdominal CT from baseline (baseline, 52 weeks)

diabetes.	Changes in lean mass from baseline using Dual Energy X-ray Absorptiometry (DXA) scan (baseline, 52 weeks)
Evaluate the effect on insulin resistance of dapagliflozin compared to glimepiride in subjects with type 2 diabetes.	Changes in hsCRP and adiponectin from baseline (baseline, 52 weeks)

2.3 Safety objectives

Safety Objective:	Outcome Measure :
Evaluate the safety of dapagliflozin and glimepiride.	Changes in CBC, electrolytes, lipid, urinalysis from baseline 52 weeks (baseline, 4, 12, 24, 36 and 52 weeks)
	Number, frequency and proportion of Subjects exposed to adverse events
	Number, frequency and proportion of Subjects exposed to hypoglycemic events

2.4 Exploratory objectives

Not applicable

3. SUBJECT SELECTION, ENROLMENT, RANDOMISATION, RESTRICTIONS, DISCONTINUATION AND WITHDRAWAL

Each subject should meet all of the inclusion criteria and none of the exclusion criteria for this study. Under no circumstances can there be exceptions to this rule.

3.1 Inclusion criteria

For inclusion in the study subjects should fulfil the following criteria:

1. Adults with T2DM (Male or female, ≥ 19 and ≤ 75 yrs)
2. Patients in insufficient glycemic control ($HbA1c \geq 7.0\%$ and $\leq 10.0\%$ in recent 4 weeks)
3. Patients with an unchanged dose of metformin ($\geq 1,000$ mg/day) for ≥ 8 weeks prior to randomization
4. Written informed consent

5. WOCBP must take precautions to avoid pregnancy throughout the study and for 4 weeks after intake of the last dose.
 - WOCBP must have a negative urine pregnancy test at screening visit WOCBP include any female who has experienced menarche and who has not undergone successful surgical sterilization (hysterectomy, bilateral tubal ligation or bilateral oophorectomy) or is not postmenopausal.
 - WOCBP must be willing to use a medically accepted method of contraception that is considered reliable in the judgment of the Investigator.

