3.2 Exclusion criteria

Subjects should not enter the study if any of the following exclusion criteria are fulfilled:

1. Type 1 diabetes or history of diabetic ketoacidosis
2. Pregnant or breast-feeding patients
3. $eGFR < 60 \text{ mL/min/1.73 m}^2$ (MDRD) on visit 1.
4. Indication of active liver disease (AST/ALT/total bilirubin $> 3 \times$ upper limits of normal) on visit 1.
5. Acute coronary syndrome, stroke or TIA within 3 months prior to randomization
6. Bariatric surgery within 2 years; treatment of anti-obesity drugs 3 months prior to randomization; any treatment leading to unstable body weight. (Unstable body weight is considered reliable in the judgment of the Investigator.)
7. Any kind of surgery using foreign metallic materials
8. History of bladder cancer or history of radiation therapy to the lower abdomen or pelvis at any time
9. History of any other malignancy within 5 years (with the exception of successfully treated non-melanoma skin cancers)
10. History of alcohol or drug abuse judged by physician within 3 months prior to randomization
11. Concomitant participation in any other clinical study.

Procedures for withdrawal of incorrectly enrolled subjects see Section 3.4.

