4. STUDY PLAN AND TIMING OF PROCEDURES

Study is planned to be conducted according to plan described in [Table 1](#).

This study is a 52-week, multi-centres, randomized, parallel-group, open, Phase IV study. All subjects will be enrolled by recruiting centres (centres treating patients with T2DM). Each enrolled subject will be referred to DXA measurement and abdominal CT scan.

The objectives of the study cover measurements at baseline, 4, 12, 24, 36 and 52 weeks. The primary efficacy end-point is to evaluate the effect of dapagliflozin 10 mg daily in

Clinical Study Protocol
Drug Substance Dapagliflozin
Study Code D1690L00067
Version 3
Date 07 June 2016

combination with metformin compared to glimepiride in combination with metformin on body composition in Korean T2DM subjects after 52 weeks of oral administration of open-label treatment.

Subjects with T2DM and inadequate glycaemic control ($\text{HbA1c} \geq 7.0\%$ and $< 10.0\%$) with stable metformin monotherapy ≥ 1000 mg/day for at least 8 weeks prior to enrolment will be eligible to enter the study.

The recruiting investigator will be the main point of contact for the subject and also responsible for the documentation of study data within the eCRF. All subjects do DXA measurement and abdominal scan scheduled to coincide with Visit 2 and Visit 7.

Local evaluation of the DXA will be conducted.

Table 1 Study Plan detailing the procedures

Study weeks	Screening (Baseline)	Randomisation	Treatment					End of Therapy	Rescue Visit ²
	0wk (-7...0 days)	0wk	4wks (+/- 7 days)	12wks (+/- 7 days)	24wks (+/- 7 days)	36wks (+/- 7 days)	52wks (+/- 7 days)	Planned if needed	
Visit	1	2	3	4	5	6	7	R	
Informed consent	0								
Demography	0								
Physical Exam ¹	0		0	0	0	0	0	0	
Medical/Surgical History	0								
Diabetes History	0								
12 lead ECG	0						0		
Height	0								
Weight	0		0	0	0	0	0	0	
BMI calculation	0		0	0	0	0	0	0	
Waist circumflex	0		0	0	0	0	0	0	
Pulse, blood pressure (SPB/DBP)	0		0	0	0	0	0	0	
FBG	0		0	0	0	0	0	0	
HbA1C	0		0	0	0	0	0	0	
CBC	0		0	0	0	0	0	0	
AST/ALT/total bilirubin	0			0	0	0	0	0	
BUN/creatinine	0			0	0	0	0	0	
Na/K/Cl	0			0	0	0	0	0	

4.1 Screening: VISIT 1

Procedures will be performed according to the Study Plan, see [Table 1](#).

Patients will obtain information regarding the study and sign informed consent for the study before any study related procedures are initiated.

Consented patients will be assessed to ensure that they meet eligibility criteria.

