Demography, medical/surgical and diabetes history will be checked, 12 lead ECG will be conducted.

Physical exam will be conducted.

Height will be measured in cm (without shoes), weight in kg (light clothes and without shoes) and waist circumference (in cm). BMI calculation will be conducted. Pulse and blood pressure (SBP, DBP) will be measured.

Laboratory baseline test for efficacy and safety parameters will be conducted: FBG, HbA1c, CBC, AST, ALT, total bilirubin, BUN, creatinine, electrolytes, total cholesterol, triglyceride, HDL-cholesterol, urinalysis, hsCRP, adiponectin. All laboratory assessment will be done in central laboratory. Pregnancy test by dipstick should be performed for all WOCBP.

All serious adverse events occurring after signing the informed consent will be reported.

Concomitant diabetes and other medications will be checked.

Eligible patients will receive an enrolment code.

4.2 Randomization: VISIT 2

Eligibility criteria will be checked.

Subjects will be randomized to the treatment arm. Subjects who do not meet these criteria must not be randomized in the study.

DXA and abdominal CT baseline measurement will be conducted.

Diet and life-style counselling will be given to the subject.

Subjects will be given a diary to record hypoglycaemic events (symptoms).

All subjects will be instructed to constantly follow hygiene to avoid urinary tract infections.

Study drug will be dispensed according to randomisation. 1mg glimepiride will be dispensed first to the subjects who are allocated to glimepiride group. Metformin will be dispensed.

All serious adverse events will be reported.

Adverse Events will be collected from subject actually taking the IP.

4.3 Treatment Period: VISITS 3, 4, 5, 6

Physical exam contains measurement of weight, waist circumflex, pulse and blood pressure. BMI calculation will be conducted.

Subject diary will be reviewed for hypoglycaemic events. New diary will be dispensed to the subjects.

Subjects will be followed for laboratory assessment of efficacy and safety according to study plan:

- Visit 3: FBG, urinalysis
- Visit 4: FBG, HbA1c, AST, ALT, total bilirubin, BUN, creatinine, urinalysis
- Visit 5: FBG, HbA1c, CBC, AST, ALT, total bilirubin, BUN, creatinine, electrolytes, urinalysis
- Visit 6 : FBG, HbA1c, urinalysis

All laboratory assessment will be done in central laboratory.

Diet and life-style counselling will be given to the subject.

Concomitant medications will be checked.

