7.7.2 Prohibited Medication

Once enrolled, subjects must not receive any of the following for the duration of the study:

- Antihyperglycaemic medication other than protocol required medication (investigational product, open-label metformin, and when necessary open-label marketed sitagliptin).
- Insulin use for up to 14 days total during the study and up to 7 continuous days is permitted only in cases where:
- Subjects are unable to take oral medication (for example during a gastrointestinal illness)
- There is a documented illness or infection that requires additional therapy for maintaining glycaemic control
- Subjects have to temporarily stop investigational product and/or open-label metformin due to requirements of this clinical study protocol.

Also, insulin use for up to 7 days during hospitalization is allowed as long as the primary reason for hospitalization is not management of the subject's glycaemic control.

- Treatment with any systemic corticosteroid therapy that will involve >7 days of therapy (two temporary periods of higher daily doses (equivalent to oral prednisolone >10 mg/day) but no longer than 7 days each are allowed). The AstraZeneca representative should be consulted prior to beginning therapy with corticosteroids for subjects who require systemic corticosteroid treatment.
- Treatment with any medication that could have an influence on bone metabolism
- Any anti-obesity medication
- Hormone replacement therapy (not including local treatment)

- Administration of sibutramine, phentermine, orlistat, rimonabant, benzphetamine, diethylpropion, methamphetamine, and/or phendimetrazine.

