## 1.2 Study design

This is a 52 weeks, randomized, open-label, parallel-group, multi-centres phase IV study to evaluate the effects of Dapagliflozin compared with Glimepiride on body composition in patients with Type 2 Diabetes inadequately controlled with Metformin. 120 participants will be randomized 1:1 to receive Dapagliflozin 10 mg qd or Glimepiride 1~2 mg qd in an open-label manner for 12 months as add-on to Metformin 1000 mg. The study design and plan are summarized in Figure 1 below and Table 1 in study protocol.

Figure 1 Study Flow Chart

Scheduled visits of the study include measurements at baseline, 4, 12, 24, 36 and 52 weeks. Subjects with T2DM and inadequate glycaemic control ( $HbA1c \geq 7.5\%$  and  $\leq 9.5\%$ ) having stable Metformin monotherapy  $\geq 1000$  mg/day for at least 8 weeks prior to enrolment will be eligible to enter the study. Subjects early terminate or complete study treatment will not be further followed after End of Treatment (EoT) Visit. Table 1 in study protocol provides a detailed schedule of assessments of events related to the study objective.

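### The entry criteria omit the metformin monotherapy condition stated elsewhere and do not exclude systemic HRT or prolonged corticosteroids, which are banned from enrolment

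*Protocol*

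**What the plan says.** Protocol section 3 tells sites that every inclusion criterion and no exclusion criterion must be met, and adds: "Under no circumstances can there be exceptions to this rule". Sections 3.3 and 3.4 repeat that only patients who satisfy the lists may be randomised.

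On background diabetes treatment, criterion 3 in Protocol 3.1 reads "Patients with an unchanged dose of metformin", at 1,000 mg/day or more, for at least 8 weeks before randomisation. Protocol section 4 instead describes patients "with stable metformin monotherapy ≥ 1000 mg/day for at least 8 weeks prior to enrolment will be eligible to enter the study", and SAP 1.2 has "having stable Metformin monotherapy".

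On other drugs, 3.2 has 11 exclusions. The only drug class it names as prior treatment is anti-obesity drugs, in item 6, which also covers "any treatment leading to unstable body weight" as judged by the investigator. Protocol 7.7.2 then states: "Once enrolled, subjects must not receive any of the following for the duration of the study". Its list includes other glucose-lowering drugs, systemic corticosteroid courses beyond 7 days (two short higher-dose periods are tolerated) and HRT other than local treatment.

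On timing, section 4.1 says of Visit 1: "Concomitant diabetes and other medications will be checked". Table 1 places that visit at most 7 days before randomisation. Section 4.2 says of Visit 2: "DXA and abdominal CT baseline measurement will be conducted".

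**The concern.** The entry lists are looser than the population described elsewhere and looser than the in-study ban, in two ways.

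- **Second glucose-lowering drug.** A patient on metformin plus another agent passes 3.1 and 3.2 as written, fails section 4, and on enrolment would have to drop the other agent under 7.7.2.
- **HRT and corticosteroids.** A long-term user passes every listed criterion and cannot comply with 7.7.2 without stopping treatment.

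No washout is provided, so a patient who stops because of enrolment does so around the baseline measurements. That patient's Week 52 change then mixes the study drug with withdrawal of the old one. This adds noise to the primary analysis of DXA fat mass and distorts the within-arm mean changes for which Protocol 8.5.1 plans confidence intervals. For dual-therapy patients it also affects HbA1c, which is measured at Visit 1 but not at Visit 2 (Protocol 5.1.7.1), so the baseline value would still reflect the dropped agent.

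Apart from the statistics, a patient may consent and qualify, and only then face stopping a long-term treatment because two lists differ.

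**Working it through.** **Comparison of the text**

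| Drug | Entry lists (3.1, 3.2) | Section 4 / SAP 1.2 | Ban in 7.7.2 |
|---|---|---|---|
| Second glucose-lowering drug | not addressed | ruled out by monotherapy | yes |
| Systemic HRT | not addressed | not addressed | yes |
| Systemic corticosteroids > 7 days | not addressed by name | not addressed | yes |
| Anti-obesity drugs | excluded (item 6) | not addressed | yes |

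The last row shows the consistent pattern, with an entry exclusion and an in-study ban together. The first three rows lack the entry exclusion.

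**Would the analysis catch these patients?** SAP 2.2 reviews eligibility failures and prohibited medication for removal from the per-protocol set. A patient who stops at entry has met the lists and breached no ban, so neither item applies.

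**Size (illustration only).** The plan offers no figure to reproduce: the sample size sections are redacted, and no prevalence, withdrawal effect or SD is given. Every input below is therefore assumed, except the 120 randomised subjects.

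Let k_up and k_down subjects stop a drug, each moving their own Week 52 change by +d or −d.

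- Mean shift: m = (k_up − k_down)·d / 120
- Added variance share: v = [(k_up + k_down)·d²/120 − m²] / SD²
- SD inflation: √(1+v) − 1
- Power: two-sided t test with 118 df and noncentrality 2.825/√(1+v), where 2.825 gives 80%

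Fat mass, with 0 to 4 HRT or steroid users who are enrolled and then stop:

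| Who stops | d (kg) | SD (kg) | m (kg) | v | Power |
|---|---|---|---|---|---|
| none | – | any | 0 | 0 | 80% |
| 1 | 1 | 2.5 | 0.008 | 0.0013 | 79.9% |
| 2, same direction | 2 | 2.5 | 0.033 | 0.0105 | 79.6% |
| 4, same direction | 3 | 2.5 | 0.10 | 0.046 | 78.2% |
| 2 up, 2 down | 3 | 2.5 | 0 | 0.048 | 78.1% |
| 4, same direction | 3 | 2.0 | 0.10 | 0.073 | 77.2% |
| 2 up, 2 down | 3 | 2.0 | 0 | 0.075 | 77.1% |
| 4, same direction | 3 | 3.0 | 0.10 | 0.032 | 78.7% |

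Example for the fourth row: m = 4×3/120 = 0.10 and v = (4×9/120 − 0.01)/6.25 = 0.29/6.25 = 0.046, so the SD rises by √1.046 − 1 = 2.3%.

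With a 60:60 split, the chance imbalance between arms has expectation zero and an SD of 0.017 kg (one subject, 1 kg) to 0.099 kg (four subjects, 3 kg, same direction).

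HbA1c, with up to 4 dual-therapy patients admitted by a site that applies 3.1 alone and an SD of 0.8 points: one subject at 0.5 points gives v = 0.0032 and m = 0.004. Four at 1.0 point, same direction, give v = 0.050 and m = 0.033.

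**The case against.** The strongest reply is that the protocol already closes most of these routes. Section 4 belongs to the same operative document and states monotherapy. Section 3 makes the lists necessary, without saying that they override section 4. Medications are checked at Visit 1, use of other glucose-lowering drugs is a ground for discontinuation in 3.9, and an investigator who reads 7.7.2 would probably not enrol someone dependent on steroids or HRT. Item 6 may catch some users. Figure 1 is not available and may itself state monotherapy. No consequence is demonstrated, since every magnitude input is assumed and the floor is zero.

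Much of this stands, and it is why the expected effect is small. It does not remove the inconsistency. The Visit 1 check has no entry criterion to apply to HRT or corticosteroids, item 6 misses a stable long-term user, and the 7.7.2 ban acts after entry. With 17 sites, different readings are foreseeable. Per-protocol handling covers patients who continue a banned drug but misses those who stop at entry.

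Two further points are fair. Section 7.7.2 also bans drugs that influence bone metabolism, which 3.2 does not exclude either. The 8-week period also runs to randomisation in criterion 3 but to enrolment in section 4 and SAP 1.2. Both suggest that the repair could go further.

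**Conclusion.** The concern holds as a low-severity point worth considering. The mismatch between the entry lists, section 4, SAP 1.2 and 7.7.2 is plain from the text. The primary between-arm comparison is not biased in expectation, because use of these drugs precedes 1:1 randomisation. Patients who are not enrolled, or who continue at a stable dose, add no withdrawal effect.

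On the assumed ranges, the loss runs from nothing to about 3 points of power, with a shift of up to 0.10 kg in the overall mean fat-mass change. If all four stoppers fell in one arm, that arm's mean would move by 4×3/60 = 0.20 kg. Confidence is high for the text comparison; the sizes are only as good as their assumptions. The case for the patient does not depend on them: nobody should qualify on the lists and then have to stop long-term treatment or breach the protocol.

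**What to change.** 1. Reword criterion 3 to require metformin as monotherapy, at 1,000 mg/day or more, with the dose unchanged for at least 8 weeks before randomisation.
2. Add one exclusion to 3.2: current systemic HRT at screening, or current or planned systemic corticosteroid treatment of more than 7 days. The sponsor should set any look-back window on clinical grounds.

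The same amendment could give the 8-week period one anchor throughout and settle whether drugs acting on bone should be an entry exclusion.

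No SAP change is needed for items 1 and 2, because the eligibility item in SAP 2.2 would then flag anyone randomised against them. The cost is one wording amendment, with the ethics review (and regulatory approval where applicable) required by Protocol 10.5, and a few more screen failures.
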